#### **Document Version History**

Version Date	Version	Author	Signature	Change Description	Reason/Comment
				Initial release.	Not applicable.

**LIST OF ABBREVIATIONS**

ARF	Acute Rheumatic fever
BPG	Benzathine Penicillin G
CI	Confidence interval
GOAL	GwokO Adunu pa Lutino ("protect the heart of a child")
GLM	Generalized Linear Model
RHD	Rheumatic Heart Disease
SAP	secondary antibiotic prophylaxis
WHF	World Heart Federation Criteria

## 2. STUDY OBJECTIVES

### 2.1. PRIMARY OBJECTIVE

To assess whether children who completed the GOAL (GwokO Adunu pa Lutino, “protect the heart of a child”) Trial and now have normal echocardiograms have the same risk for progression as a new group of age and sex matched controls who have a normal echocardiogram at study entry.

**Aim 1:** Compare the two-year risk of echocardiographic progression between children and adolescents who completed the GOAL Trial with a normal echocardiogram (that is, a prior diagnosis of latent RHD) and age and sex matched controls with repeated normal echocardiograms (normal in both the original GOAL screening in 2017/2018 and in the GOAL-Post screening in 2021).

**Hypothesis:** The risk of RHD development (2012 World Heart Federation [WHF] Criteria) in children and adolescents who have had normalization of their echocardiogram following latent RHD diagnosis is not higher than children and adolescents without prior documentation of latent RHD.

**Clinical application:** We are trying to answer the question: “Is it safe to take these children off Benzathine Penicillin G (BPG) after two years if they do not show latent RHD?”

### 2.2. SECONDARY OBJECTIVES

**Aim 2:** Determine the five-year rate of RHD progression and regression among children with persistent latent RHD who receive secondary antibiotic prophylaxis (SAP) - medium-term impact of prophylaxis. The five-year period includes time from initial GOAL enrollment to the end of GOAL-Post.

**Clinical application:** We are trying to determine the durability of the intervention to prevent RHD progression.

**Additional aims (for participants with normal echocardiograms) (AIM 1):**

To assess the risk for RHD progression among children who completed the GOAL Trial and now have normal echocardiograms.

To assess the risk for progression among a new group of age/sex/geography matched controls who have a normal echocardiogram at study entry.

### 3. BACKGROUND/INTRODUCTION

The GOAL Trial reached completion in October 2020, finding that SAP resulted in a significant and substantial reduction in RHD progression among children with latent, or screen-detected RHD. These data have important clinical and public health implications. However, the GOAL Trial also showed that approximately 50% of children with latent RHD regressed at two-years, with the majority (85%) returning to a normal echocardiographic study with or without antibiotic prophylaxis. These results raise questions on the recommended duration of prophylaxis for latent RHD, with no current evidence to guide practice for this group.

GOAL-Post is two prospective extension studies that build on the infrastructure (case managers and peer groups) and success (98% retention and 99% BPG adherence) of the GOAL Trial.

#### 3.1. STUDY DESIGN

GOAL-Post includes two observational studies to investigate outcomes for participants who completed the GOAL Trial, divided by final GOAL diagnosis: 1. *normal* or 2. *persistent latent RHD*. GOAL-Post will include former GOAL Trial participants (96% retention in care), as well as an age and sex matched cohort for Aim 1.

[figure not shown]

Figure 1: Design of GOAL-Post

GOAL-Post	Statistical Analysis Plan
Version 1 – 2 July 2024	

### **3.2. TREATMENT GROUPS**

The following treatment groups are identified within GOAL-Post:

- Never diagnosed with latent RHD (negative at screening for GOAL, and negative when screened for GOAL-Post) – Group 1B. This group has never received SAP.
- Randomized in the GOAL Trial to SAP and normal echocardiogram (no latent RHD) at the 2-year endpoint of the GOAL Trial and at the start of GOAL-Post. (Children who had SAP for two years and are then taken off SAP given a normal echocardiogram and no sign of latent RHD.)
- Randomized in the GOAL Trial to SAP and latent RHD at the start of GOAL-Post.
- Randomized in the GOAL Trial to control and normal echocardiogram (no latent RHD) at the 2-year endpoint of the GOAL Trial and at the start of GOAL-Post, these participants never received SAP.
- Randomized in the GOAL Trial to control and latent RHD at start of GOAL-Post. These participants did not receive SAP in the GOAL Trial but did receive SAP in GOAL-Post.

### **3.3. STUDY POPULATION**

**Aim 1** planned to enrol between 953 and 1102 participants, a maximum of 364 participants with normal echocardiograms after 2-years of participation in the GOAL Trial (Group A) and an appropriate number of age and sex matched controls (Group B, see sample size) without echocardiographic evidence of RHD.

**Group A:** Children and adolescents were eligible for Aim 1 if they

- (1) are a prior GOAL Trial participant deemed by the adjudication panel to have a normal echocardiogram at the 2-year endpoint,
- (2) are not receiving SAP, and
- (3) agree to participate in the study via the study's informed consent/assent process.

**Group B:** Children and adolescents were eligible for Aim 1 if they

- (1) have a normal echocardiogram at the start of the study,
- (2) meet the age and sex match requirement (from former GOAL Trial participants), and
- (3) have agreed to participate in the study via the study's informed consent/assent process.

**Aim 2** planned to enrol up to 415 participants with persistent latent RHD after 2 years of participation in the GOAL Trial. Children and adolescents were eligible for Aim 2 if they

- (1) were a prior GOAL Trial participant deemed by the adjudication panel to have persistent latent RHD on echocardiogram at the 2-year endpoint,
- (2) have been prescribed SAP (BPG), and
- (3) agree to participate in the study via the study's informed consent/assent process.

### **3.4. SAMPLE SIZE**

**Aim 1:** A sample size of between 953 and 1102 participants (up to 350 and as few as 291 participants with normal echocardiograms after the GOAL Trial and up to 811 age and sex matched controls) will be needed, assuming up to 10% loss to follow-up and that 2% of the control group (Group B), and 3% of the children who completed the GOAL Trial (Group A) will develop RHD.

A two-group large-sample normal approximation test of proportions with a one-sided 2.5% significance level will have 80% power to reject the null hypothesis of a difference in proportions of <2% in favor of the alternate hypothesis that the proportion of the two groups are equivalent. Calculation was done using nQuery 8 (Statistical Solutions Ltd). This sample size was increased by 10% to account for loss to follow-up.

GOAL-Post	Statistical Analysis Plan
Version 1 – 2 July 2024	

**Aim 2** does not include a comparator group and will include the maximum number of former GOAL Trial participants with persistent latent RHD (currently 415 retained in care).

For Aim 1 Group A we plan to enrol all the participants who were enrolled in the GOAL Trial, meet the eligibility criteria and are willing to be enrolled in the GOAL-Post extension study. The maximum number that can be enrolled in group A is 364 who had normal echocardiograms at the end of the GOAL Trial. If this maximum number is enrolled, and there is 10% loss to follow-up in GOAL-Post, we need to enrol 589 participants in Group B. This gives a total sample size of 953.

Since there is only a fixed number of children who qualify for enrolment into Group A, we determined the size of Group B after group A has been enrolled. The size of Group B was determined to give 80% power, given the size of Group A, under the previous assumptions. The smallest sample size for Group B is given above. If 90% of the original cohort are enrolled in Group A, the size of Group A will be 328 and the size of Group B will be 666 for a total sample size of 994. If only 80% of the original cohort are enrolled in Group A, the size of Group A will be 291 and the size of Group B will be 811 for a total sample size of 1102.

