## 6. STATISTICAL METHODOLOGY

### 6.1. AIM 1 PRIMARY ANALYSES

We will report the proportion of children who develop echocardiographic evidence of RHD in each of Group A and B (never diagnosed with latent RHD; negative at screening for GOAL, and negative when screened for GOAL-Post). We will fit a generalized linear model (GLM) with an identity link and binomial distribution, adjusted for the matching factors age and sex to estimate the difference in proportion of children who develop echocardiographic evidence of RHD, with a 95% confidence interval (CI), between Groups A and B.

To assess whether this difference in proportion between the two groups is < 2% we will evaluate the upper bound of the estimated 2-sided 95% CI for the difference in proportions calculated from the GLM. If this CI does not include a difference larger than 2%, the risk for development of RHD will be assessed to be similar in the two groups of participants.

Children with confirmed Acute Rheumatic fever (ARF) and children who develop echocardiographic evidence of RHD prior to the 2-year endpoint will be counted as having reached the primary study endpoint (development of RHD).

We will also repeat the analysis, using the same statistical methods, but restricting the analysis to only the subgroup of children who were randomized to the BPG arm in the GOAL Trial. This will reduce the sample size and power, therefore we do not expect to be powered to show statistically significant results, but will provide all estimates to serve for hypothesis generation.

The results of the side-by-side comparison of echocardiograms will be summarized.

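### Aim 1: the 80% power in section 3.4 does not follow from its written risks (Group A 3%, Group B 2%), which give about 14%; the planned sizes fit those risks swapped

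*SAP*

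**What the plan says.** Section 3.4 gives the planning assumptions for the Aim 1 comparison: "2% of the control group (Group B), and 3% of the children who completed the GOAL Trial (Group A) will develop RHD", a one-sided 2.5% large-sample normal test of two proportions, a 2-point difference, and 10% loss to follow-up. The test "will have 80% power to reject the null hypothesis of a difference in proportions of <2% in favor of the alternate hypothesis" of equivalence.

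Group A is limited to former GOAL participants with a normal echocardiogram, so "we determined the size of Group B after group A has been enrolled". The section adds: "The size of Group B was determined to give 80% power, given the size of Group A, under the previous assumptions". Three cases follow, as enrolled A/B: 364/589, 328/666 and 291/811.

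The direction is set elsewhere. The hypothesis in section 2.1 is that the risk in Group A "is not higher than children and adolescents without prior documentation of latent RHD". Section 6.1 looks at the upper bound of the two-sided 95% CI for the difference: "If this CI does not include a difference larger than 2%, the risk for development of RHD will be assessed to be similar".

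**The concern.** This is a non-inferiority comparison of an adverse outcome. Success means that the upper bound for A minus B stays at or below 2 points. The written risks put the true difference at +1 point, so only 1 point is left before the margin. With about 260 to 330 evaluable children in Group A and risks of 2–3%, the standard error is itself more than 1 point, so 80% power looked impossible.

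Aim 1 asks whether prophylaxis can safely stop in children whose echocardiogram has become normal. An unmet criterion from a study with 80% power reads very differently from one with 14% power. If the 80% was instead obtained with a lower risk in Group A than in controls, the claim rests on a favourable assumption that the text does not disclose and in fact reverses.

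**Working it through.** **Inputs.** From section 3.4: pA = 0.03, pB = 0.02, one-sided 2.5% (z = 1.96), 80% power (z = 0.8416), 10% loss, and the three size pairs. From section 6.1: margin 0.02, upper bound of A minus B. Evaluable n = 0.9 × enrolled, rounded to 328/530, 295/599 and 262/730.

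**Formula** (unpooled normal approximation):

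SE = √[pA(1−pA)/nA + pB(1−pB)/nB]

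power = Φ((0.02 − (pA − pB))/SE − 1.96)

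**1. Written risks (A 3%, B 2%).** The distance to the margin is 0.02 − 0.01 = 0.01. For 364/589, SE = √(0.0291/328 + 0.0196/530) = 0.0112, so power = Φ(0.892 − 1.96) = 14.3%. For 80% power the distance would have to be 1.96 + 0.8416 = 2.8016 standard errors.

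| Enrolled A/B | SE (points) | Distance/SE | Power |
|---|---|---|---|
| 364/589 | 1.12 | 0.89 | 14.3% |
| 328/666 | 1.15 | 0.87 | 13.8% |
| 291/811 | 1.17 | 0.85 | 13.4% |

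**2. Other methods, same risks and sizes.** The section does not name the variance formula, so several were tried.

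| Method | 364/589 | 328/666 | 291/811 |
|---|---|---|---|
| Exact power of the Wald interval | 18.0% | 18.7% | 19.3% |
| Farrington-Manning | 11.5% | 10.6% | 9.7% |
| Exact power of the Newcombe interval | 11.0% | 9.5% | 8.8% |

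A pooled variance gives 16.3–17.5%. Assuming no loss at all gives 14.4–15.4% (unpooled). None comes near 80%.

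**3. Could a larger Group B rescue it?** No. With an unlimited Group B and 328 evaluable in Group A, SE = √(0.0291/328) = 0.00942 and power = Φ(0.01/0.00942 − 1.96) = 18.5% (23.1% by exact Wald). Reaching 80% with an unlimited Group B would need nA = 0.0291/(0.01/2.8016)² ≈ 2,284 evaluable, and "The maximum number that can be enrolled in group A is 364".

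**4. What reproduces the plan's sizes?** Exchange the risks (A 2%, B 3%). The distance becomes 0.02 + 0.01 = 0.03, and power is 80.0%, 79.9% and 80.0% at the three pairs (exact Wald 78.6%, 77.6%, 77.5%). Solving for Group B:

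nB = 0.0291/[(0.03/2.8016)² − 0.0196/nA], then divide by 0.9

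| nA evaluable | nB evaluable | nB enrolled | Stated |
|---|---|---|---|
| 328 | 530 | 589 | 589 |
| 295–296 | 601–603 | 667–670 | 666 |
| 262 | 730 | 811 | 811 |

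Over a grid of risk pairs from 0.5% to 5.5% in 0.5-point steps, only A 2%/B 3% lies within 0.2 points of 80% at all three sizes. The nearest other pair, A 3.5%/B 5.5%, gives 80.5%, 80.5% and 80.7% and matches no figure in the plan.

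**5. Is it only a sign slip?** Keeping A 3%/B 2% and testing in the opposite direction gives 76.3%, 74.5% and 72.4%. That does not reproduce the plan.

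**6. Equal risks of 2%.** Power is 52.9%, 52.0% and 50.9% (exact Wald 54.8%, 54.5%, 53.4%).

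**7. Two further slips in section 3.4.** The null is worded as a difference below 2%, which is what section 6.1 sets out to show. The Group A range is given as "up to 350 and as few as 291 participants with normal echocardiograms after the GOAL Trial", whereas the same section and section 3.3 give a maximum of 364, and the total of 953 is 364 + 589.

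**The case against.** The strongest reply is that this is probably a transposition in the text. The swapped risks fit the sizes so well that the study may never have been planned at 14%; the low figure applies only if A 3%/B 2% was the real expectation. That stands: what is established is that the written risks and the stated power are incompatible, not that the study's true power is 14%. But the likely explanation is no comfort, because it means the 80% assumes a lower risk in children with prior latent RHD, and the SAP nowhere says so.

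Second, the error leaves the analysis intact. Group B has already been sized, and section 6.1 compares an interval with a fixed margin without using the planning risks. This is also right. Neither the estimate nor the type I error is affected; the harm is to the stated power and to the reading of an unmet criterion.

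Third, some details are loose. The variance formula is not named, so 14% is one variant among several. The middle pair back-solves to 667–670 rather than 666. The match needs division by 0.9; multiplying by 1.1 gives slightly smaller numbers. The calculations are unadjusted, whereas the primary model adjusts for age and sex. All true, but nothing in the plan suggests that any of these could bridge the gap from 9–19% to 80%.

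The 350 may reflect the 96% retention in section 3.1 (0.96 × 364 = 349.4). The SAP does not say so, and the two maxima still disagree.

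**Conclusion.** The concern holds. Under the risks written in section 3.4, power for the primary Aim 1 comparison is about 14% (unpooled normal approximation), with a range of 8.8% to 19.3% over the other methods, against 80% stated. If those risks were intended, failing the criterion is the expected result. If the swapped risks were used, the 80% is arithmetically correct but depends on Group A being 1 point below never-diagnosed controls; at equal 2% risks it falls to about 51–53%.

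These figures assume 10% loss in both groups, the 2-point margin, one-sided 2.5% and no covariate adjustment. The document alone cannot settle which element was transposed. Because the stated power of the primary analysis is wrong as written, this must be corrected.

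**What to change.** All changes are in section 3.4.

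1. Check the nQuery file for the risks, group labels and direction entered, and make the written assumptions match what was used and intended.
2. If A 3%/B 2% was intended, replace the 80% claim with about 14%, naming the unpooled normal approximation, and give 18–19% for the exact Wald interval. If A 2%/B 3% was used and intended, write that, and state that the 80% depends on a lower risk in Group A than in never-diagnosed controls. Adding the power at equal 2% risks (about 51–53%) is not needed to remove the contradiction, but it would show readers how much rests on that assumption.
3. Write the null as A minus B of at least 2 points and the alternative as A minus B below 2 points.
4. Reconcile the Group A maximum of 350 with 364.

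The cost is one file check and a few sentences. Enrolment, the margin, the model and the rule in section 6.1 do not change. The stated power may become less favourable.

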### 3.5. STUDY PROCEDURE

**Table 1: Aim 1 GOAL-Post Assessment Schedule**

	Enroll	Year 1 Follow-up				Year 2 Follow-up				Final Visit
	Q0	Q1	Q2	Q3	Q4	Q5	Q6	Q7	Q8	
Informed Consent/Assent	X									
Demographics	X*									
Medical History	X*									
Family History	X*									
Concomitant Healthcare		X		X		X		X		X
Echocardiogram	X**				X					X

\*Only Aim 1, Group B as these data are already collected for former GOAL Trial participants  
\*\* Will use GOAL end of trial echocardiogram for Aim 1, Group A and obtain a full echocardiogram for Aim 1, Group B participants during the enrollment visit.

**Table 2: Aim 2 GOAL-Post Assessment Schedule**

	Transitional Year (Year 3 follow-up)				GOAL-Post Year 1 (Year 4 follow-up)				GOAL-Post Year 2 (Year 5 follow-up)				Final Visit
	Q1	Q2	Q3	Q4	Q5	Q6	Q7	Q8	Q9	Q10	Q11	Q12	
Informed Consent/Assent		X			X								
Concomitant Healthcare	X		X		X		X		X		X		X
BPG Diary	X	X	X	X	X	X	X	X	X	X	X		
Adverse Events	X	X	X	X	X	X	X	X	X	X	X		
Echocardiogram	X*				X				X				X

\* GOAL end of trial echocardiogram.

## 4. POPULATIONS OF ANALYSIS

For **Aim 1** the analysis population will be all participants enrolled in Aim 1 in GOAL-Post. The Aim 1 Group A population is defined as GOAL-Post consent completed, arm 1 selected, and GOAL-Post enrolment echo is normal. The Aim 1 Group B population is defined as GOAL-Post consent completed and arm 4 selected.

For **Aim 2** the analysis population will be all participants enrolled in Aim 2 in GOAL-Post. The Aim 2 population is defined as GOAL-Post consent completed and arm 2 selected, or GOAL-Post consent completed, arm 1 selected, and GOAL-Post enrolment echo is not normal.

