## 5. OUTCOME VARIABLES

All Aim 1 echocardiograms will undergo blinded review by a panel of 2 cardiologists (2012 WHF guidelines), consisting of pre-review by 2 of these cardiologists (to guide discussion) and final consensus determination by the panel. A side-by-side comparison of the echo done at the end of the GOAL Trial and the end of GOAL-Post will also be done. Echocardiograms will be reviewed with side-by-side two-year (completion of the GOAL Trial) and five-year (end of GOAL-Post) echocardiograms presented to the panel, with random right or left display. The panel will be blinded to timing of the echocardiograms and will determine if the studies were “the same”, “right worse” or “left worse” by application of strict operational definitions, defined in the GOAL Trial.

The primary outcome of **Aim 1** will be development of echocardiographic evidence of RHD (2012 WHF Criteria) among children and adolescents with a normal echocardiogram at the 2-year endpoint in the GOAL Trial and upon enrolment into GOAL-Post (variable enollecho).

An **alternative outcome** for **Aim 1** is worsening on a side-by-side comparison of the echo done at the end of the GOAL Trial and the end of the GOAL-Post trial. These will be assessed as same, progressed or regressed. This is done only for Group A. This is captured in the database as a combination of two variables. If eligible\_echo\_comparison is “no” then the result is “same”. If eligible\_echo\_comparison is “yes” then the result is captured in the variable side\_by\_side results. The final diagnosis is given as the variable final\_diagnosis\_after\_comparison. Again this variable is a combination of two variables . If eligible\_echo\_comparison is “no” then the result is “normal”.

The primary outcome of **Aim 2** will be echocardiographic progression and regression among children who had persistent latent RHD at the end of the GOAL Trial. This will be variable enollecho from Period 26.

Progression is defined as progression of echocardiographic features of latent RHD to include:

- New pathological regurgitation at a previously unaffected valve
- Worsening grade of existing mitral or aortic regurgitation (mild, moderate, severe)
- Development of two morphological features consistent with RHD (2012 WHF criteria) at a valve that previously had normal morphology or the addition of one morphological feature at a valve previously only showing a single morphological abnormality.

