**Table 4: Proportion with progression and regression in Group A**

	Proportion (95% CI)
Proportion worsened (progressed)	
All participants in Aim 1	
Only participants randomized to the BPG arm in the GOAL Trial	
Proportion better (regressed)	
All participants in Aim 1	
Only participants randomized to the BPG arm in the GOAL Trial	

Group A: Children who completed the GOAL Trial and have normal echocardiograms in GOAL-Post

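### Group A has two incompatible baseline rules: Table 1 uses the end-of-GOAL echocardiogram, while sections 3.2, 4 and 5 require a further normal one at GOAL-Post enrolment

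*SAP*

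**What the plan says.** All references are to the SAP.

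- **Section 3.5, Table 1 footnote:** "Will use GOAL end of trial echocardiogram for Aim 1, Group A and obtain a full echocardiogram for Aim 1, Group B participants". A new study at enrolment is scheduled for Group B only.
- **Section 3.2** describes the former GOAL participants without latent RHD as having a "normal echocardiogram (no latent RHD) at the 2-year endpoint of the GOAL Trial and at the start of GOAL-Post", that is, at two time points.
- **Section 5** sets the Aim 1 primary outcome among "children and adolescents with a normal echocardiogram at the 2-year endpoint in the GOAL Trial and upon enrolment into GOAL-Post".
- **Section 4:** "The Aim 1 Group A population is defined as GOAL-Post consent completed, arm 1 selected, and GOAL-Post enrolment echo is normal". It sends arm 1 children whose enrolment study is not normal to the Aim 2 population.
- **Section 8, Table 4 footnote:** "Group A: Children who completed the GOAL Trial and have normal echocardiograms in GOAL-Post".
- **Sections 3.3 and 3.4** are silent on a second study. Eligibility asks that the child be "deemed by the adjudication panel to have a normal echocardiogram at the 2-year endpoint", and the size limit reads "The maximum number that can be enrolled in group A is 364 who had normal echocardiograms at the end of the GOAL Trial".

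The alternative Aim 1 outcome, reported in Table 4, is "worsening on a side-by-side comparison of the echo done at the end of the GOAL Trial and the end of the GOAL-Post trial". Section 5 labels those two studies as year 2 and year 5. Section 2.1 calls the Aim 1 comparison a two-year risk.

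**The concern.** The Table 1 footnote and sections 3.2, 4 and 5 cannot all be followed as written. The choice decides which children are in Group A and when their time at risk begins, and each choice has its own cost.

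- **If Table 1 governs**, Group A's risk period includes the gap between the end of GOAL and GOAL-Post enrolment. Group B's does not.
- **If section 4 governs**, a child who was normal at the end of GOAL and abnormal at enrolment leaves Group A. The rule in section 6.1 that counts RHD found before the two-year endpoint cannot reach a child outside the analysis population. Table 4 measures change from the end of GOAL, but only in children selected on a later normal study.

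Section 2.1 frames the clinical question as the safety of stopping prophylaxis after two years. RHD found at enrolment is the earliest evidence on that question, so the plan should say where it is reported.

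**Working it through.** The plan gives no count of children who became abnormal in the gap and no gap length per child, so it has no figure of its own to reproduce. What follows is a range under stated assumptions.

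**Inputs**
- Two-year risk r: 2% and 3%, borrowed from section 3.4, which gives no time span for them.
- Margin: 2 percentage points (section 6.1).
- Gap g: GOAL ended in October 2020 (section 3) and GOAL-Post screening was in 2021 (section 2.1). If Group A enrolled alongside that screening, g runs from 2 months (31 October 2020 to 1 January 2021) to 15 months (1 October 2020 to 31 December 2021). It is longer for a child whose last GOAL study came earlier. The plan's year labels imply 5 − 2 − 2 = 1 year.
- Return to normal: section 3 reports about 50% regression at two years, 85% of it to normal. 0.50 × 0.85 = 0.425, about 42%.
- Constant hazard: risk over t years = 1 − (1 − r)^(t/2).

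**If Table 1 is followed.** Group A is at risk for g + 2 years and Group B for 2 years. With r = 2% in both groups:

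| Gap | Group A risk | Group B risk | Spurious excess |
|---|---|---|---|
| 2 months | 2.165% | 2% | +0.16 points |
| 6 months | 2.494% | 2% | +0.49 points |
| 12 months | 2.985% | 2% | +0.98 points |
| 15 months | 3.230% | 2% | +1.23 points |

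**If section 4 is followed.** Expected number of children becoming abnormal in the gap = 364 × [1 − (1 − r)^(g/2)], g in years, if all 364 enrol:

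| Gap | r = 2% | r = 3% |
|---|---|---|
| 2 months | 0.6 | 0.9 |
| 6 months | 1.8 | 2.8 |
| 12 months | 3.7 | 5.5 |
| 15 months | 4.6 | 6.9 |

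Effect on Table 4 with a one-year gap:
- r = 2%: gap risk 1 − 0.98^0.5 = 1.005%; year-2-to-year-5 risk 1 − 0.98^1.5 = 2.985%. After the enrolment filter the table shows 2%. Understatement if changes persist: 0.98 points. If 42.5% of the gap cases return to normal: 2.985 − 0.425 × 1.005 = 2.56%, an understatement of 0.56 points.
- r = 3%: gap risk 1.511%; year-2-to-year-5 risk 4.466%, against 3% shown. Understatement if changes persist: 1.47 points. With return to normal: 4.466 − 0.425 × 1.511 = 3.82%, an understatement of 0.82 points.

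**Aim 2 membership.** Section 4 adds arm 1 children with an abnormal enrolment study. Section 3.3 requires persistent latent RHD at the GOAL two-year endpoint, and section 5 defines the Aim 2 outcome among children who had it at the end of GOAL. If arm 1 is the group normal at the end of GOAL, as its use for Group A suggests, these children do not qualify. The progression categories in section 5 start at borderline or definite disease, so a change from normal has no place in them. Sections 3.2 and 6.3 and Table 7 group by status at the start of GOAL-Post, which agrees with section 4. The plan therefore differs with itself here too.

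**The case against.** The strongest defence is that section 4 describes a sound design. The primary objective concerns children who now have normal studies, and Group B must also be normal twice, in 2017/2018 and in 2021. A contrast from the end of GOAL would have no matching time zero in Group B. All of this stands, and the primary contrast on that reading needs no change.

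It may also be said that the enrolment echocardiogram in section 4 simply is the end-of-GOAL one, with the Aim 2 clause correcting a wrong arm selection. That is possible, but sections 3.2 and 5 name two separate time points, and the unequal time at risk would then apply.

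A reader might infer more than the document supports:
- **That section 3.3 or the 364 contradicts section 4.** They state eligibility and a ceiling. Both are compatible with a narrower analysis population.
- **That the children who became abnormal are lost.** Target-GOAL (sections 6.1 to 6.3 aside, this is the section 6.2 exploratory analysis) counts RHD at any time and reports proportions by GOAL arm and two-year status. Tables 5 and 7 also carry a row for all children normal at the end of GOAL. The children are absent from Table 4 and from any contrast with Group B, not from the report.
- **That the primary test could falsely reassure.** Section 4 selects both groups in the same way, and the Table 1 rule works against meeting the margin.
- **That power would collapse if gap cases were counted.** That calculation needs an assumed share of gap cases and adds them to Group A alone.
- **That arm 1 is undefined.** Figure 1 is not shown and the arm codes may be explained elsewhere.

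Table 4's footnote does disclose that Group A is normal in GOAL-Post. It does not say that children normal at the end of GOAL have been removed.

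**Conclusion.** The contradiction between the Table 1 footnote and sections 3.2, 4 and 5 is real, and it changes the Aim 1 population and time zero.

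- **Under Table 1**, the comparison would not be a two-year risk. The spurious excess in Group A is about 0.2 to 1.2 points for gaps of 2 to 15 months, and about 1.0 at 12 months. This rests on a constant hazard, equal 2% risks and enrolment of Group A alongside the 2021 screening.
- **Under section 4**, the primary contrast stands. Table 4 tends to understate worsening since the end of GOAL: with a one-year gap, by about 1.0 to 1.5 points if changes persist and about 0.6 to 0.8 points if about 42% return to normal. The number of children involved is small, and a shorter gap gives less. The Aim 2 population would also include children who do not meet the condition in sections 3.3 and 5.

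The actual gap and the actual number of such children are not in the plan, so these figures show a plausible size and are not estimates.

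**What to change.** 1. Reconcile the Table 1 footnote with sections 3.2, 4 and 5, and state one baseline-echocardiogram rule and one time zero for Group A.
2. If Group A had no separate enrolment study, compare the groups over equal follow-up or per person-year.
3. If it had one:
   - report how many children were normal at the end of GOAL and abnormal at enrolment;
   - give the Table 4 side-by-side proportion also in all children normal at the end of GOAL, split by GOAL arm;
   - reconcile the Aim 2 clause in section 4 with sections 3.3 and 5, and report those children separately from the main Aim 2 result.

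The cost is some rewording and a little extra analysis on data already held. The additional Table 4 figure is likely to be slightly less favourable.
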